2.1 Background and study rationale

a. Pregnancy of unknown location and Ectopic pregnancy

Pregnancy of unknown location (PUL) is a syndrome of early pregnancy composed of a positive urine pregnancy test without the visualisation of a pregnancy on trans-vaginal ultrasound (TVUS). There are four possible final diagnoses from PUL: intrauterine pregnancy (IUP); failing pregnancy of unknown location (FPUL); persistent pregnancy of unknown location (PPUL); and ectopic pregnancy (EP) [1].

The initial investigation that is currently performed with TVUS is serum beta human chorionic gonadotrophin (BhCG) testing. Previous studies however have highlighted that the traditional single serum hCG testing following TVUS is a poor predictor of outcome, viability and location of PUL [3].

b. BhCG monitoring and modelling

hCG (a glycoprotein produced by syncytiotrophoblast cells responsible for maintaining the corpus luteum in early pregnancy). hCG is hetrodimeric and consists of an alpha and beta subunit. The beta subunit is unique to hCG and is therefore clinically useful in pregnancy. The use of beta hCG (BhCG) and progesterone levels in the management of PUL is commonplace [4-5]. However, interpretation of the results can be subjective [6-7].

A statistical logistical regression model which utilised initial BhCG levels and BhCG ratio (48hour BhCG divided by 0 hour BhCG) was created by a research group with the aim of allowing PUL to be safely risk stratified [8-14]. This has been validated and found to be superior to isolated progesterone and BhCG protocols, although unclear how applicable this may be to populations such as the United States [14-15]. A modified and validated model has since been trialled and used in a multi-centre study across North West London in order to optimise PUL risk stratification into 'low risk' (encompassing IUP and FPUL) and 'high risk' (encompassing PPUL and EP) [2]. This was part of the Assessment of Biomarkers and Ultrasound in Pregnancy of Unknown Location and Ectopic Pregnancy study (ABPEP) which utilised serial BhCG observation (at 0 hours and 48 hours from diagnosis of PUL), BhCG ratio along with progesterone testing [2].

This model has come to be known as the 'M6 model' and was developed from a cohort of 2753 cases of PUL. It classified 62.1% PUL as 'low risk' with a negative predictive value of 98.6% [2]. This the model which we currently adopt in our unit.

SOUL, VERSION 5

September 2021

c. Point of care BhCG testing

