BhCG measurements require serum samples sent to hospital laboratories in order to assess levels in a standardised manner. However, point of care (POC) BhCG testing is now available that uses whole blood to provide lab-quality, quantitative results in minutes. This could lead to a reduction in time waiting for results as well as a reduction in the associated psychological distress to patients and their partners [16]. The only food and drug agency approved quantitative test is the i-STAT BhCG (Abbott POC) test that could play a role in providing quick results that are comparable to hospital laboratory analysis. This could therefore be used to risk stratify within a risk prediction model [17]. The Abbott POC test is CE marked, confirm its conformity with European standards for health and safety of products sold within the European Economic area.

d. Anxiety and Depression related to Early Pregnancy Loss

Anxiety, depression and post-traumatic stress disorder (PTSD) are recognised complications following early pregnancy loss. A systematic review of 27 papers exploring the psychological impact of early pregnancy loss identified significant depression and anxiety within the first month, with 8-20% moderate depression and 18-32% anxiety reported at 4-6 weeks [18]. A Cochrane review of six studies involving 1001 women demonstrated no single beneficial method of managing the psychological impact of early pregnancy loss, but that counselling may be beneficial [19]

A UK study of 160 women demonstrated that uncertainty in diagnosis, rather than the negative or positive connotations of the diagnosis itself, was a greater contributing factor in women's feelings of anxiety and depression in relation to PUL [20]. Furthermore, a local pilot study demonstrated women experiencing both miscarriage and ectopic pregnancy fulfilled criteria for PTSD, with many suffering from moderate-to-severe anxiety and depression, with psychological morbidity persisting at least 3 months following pregnancy loss [21].

e. The Hospital and Anxiety Depression Scale

The Hospital Anxiety and Depression Scale is a 14-part questionnaire with 7 questions exploring symptoms of anxiety and depression respectively. Each question is answered with a scale of 0-3 to represent severity of symptoms, with an independent maximum score of 21 for depression or anxiety. A score \geq 11 is deemed moderate, whilst \geq 16 represents severe symptoms [22].

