4.9 Method of study

This is a cohort study and will recruit patients in the first trimester (less than 14 weeks gestation) and their partners who meet the inclusion criteria attending the Early Pregnancy Unit. There will be two phases of the study, each with a minimum duration of 4 months. Phase 1 aims to establish the psychological burden of PUL under the existing care pathway, whilst phase 2 introduces point of care BhCG testing in clinical practice. The phases of the study are described in more detail below.

An information leaflet detailing the purpose of the study will be provided, and separate patient information sheets will be used for each phase of the study. A minimum of 15 minutes will be provided for patients to read the study information with the research team not present. Patients will then have opportunity to elicit further information or clarification from the research team. There are no significant ethical, legal or management issues. Women who both verbally consent and consent in writing will follow a well-defined pathway (see flowchart appendix).

The phases of the study are

- Group 1: Assessing the psychological impact of pregnancy of unknown location (PUL) classification pending a final diagnosis. Confirming the reliability of point of care testing in correlation with laboratory BhCG levels (gold standard).
- Group 2: To assess if shortening time to providing patients classified with PUL with results and advice using point-of-care beta human chorionic gonadotrophin (BhCG) testing reduces psychological burden.

Women with symptoms in the first trimester are routinely seen in the Early Pregnancy Unit (EPU). A clerking proforma is completed, urine is tested and a transvaginal ultrasound scan is performed. Blood testing and follow up arrangements are made if required with blood results inputted into a validated statistical model if a patient is classified with a PUL.

Participants in phase one of the study will not be provided with the POC BhCG result. They will await the laboratory result. Simultaneously we will ascertain reliability of POC in clinical practice during this time.

Patients in phase two will be provided with the POC test result, which will reduce the time to which they receive the result. Prior to transfer from phase 1 to phase 2 of research, correlation between POC and laboratory BhCG levels will be calculated in order to confirm its reliability by creating a correlation curve using the data.

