Patients and partners will be asked to complete the questionnaire at three time points: 1) On classification of PUL at time zero once blood is taken, 2) at the 48-hour time point after blood is taken (if 48-hour bloods are required for the patient); and 3) after definitive diagnosis and management.

The maximum number of questionnaires that will be completed will be 6: 1 for each time point for the patient and 1 for each time point for the partner.

The questionnaires for the first two time points will be offered electronically whilst the patient is having their blood sample taken via use of a quick response matrix barcode (QR code). The third time point HADS will be texted through the encrypted system Accurx. We will contact the patient a maximum of 3 times to complete the questionnaire at the third time point to reduce loss of follow up.

The results will be submitted electronically each time. The results will be reviewed on a weekly-biweekly basis by the research team.

If patients score for moderate to severe anxiety or depression at any time point, we will call the patient. If they are struggling with their PUL classification or diagnosis, we will advise them to make an appointment to see their GP as soon as possible to arrange appropriate follow up, whilst clarifying any ongoing follow up at the early pregnancy unit. If patients score for moderate to severe anxiety or depression at any time point where no further follow up at the unit is indicated, we will also ask permission to send a text over Accurx that will list information relating to local miscarriage support groups, Tommy's Miscarriage charity, Petals Baby Loss Counselling Charity, the Ectopic Pregnancy Trust, the Miscarriage Association and Improving Access to Psychological Therapists (IAPT). If further support is required, they will be advised to contact their GP as soon as possible.

a. Symptoms

Patients will be asked to complete the standard clerking proforma used within the unit, including demographic data and information regarding previous obstetric, medical and gynaecological history and questions regarding symptoms.

b. Ultrasound

Trans-vaginal ultrasound is then performed as part of standard practice. Women with a PUL will be identified as eligible for the study

Any ultrasound abnormality detected will be managed in accordance with local and national guidance. Follow up trans-vaginal ultrasound for all will be arranged as per routine clinical practice if required.

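### The check before phase 2 is a correlation, which cannot by itself show that POC BhCG agrees with laboratory BhCG; no bias estimate, limits of agreement or acceptable difference is planned

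*Combined protocol and SAP*

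**What the plan says.** Section 4.9 (Method of study) gives phase 1 two purposes. One is psychological. The other is "Confirming the reliability of point of care testing in correlation with laboratory BhCG levels (gold standard"). Phase 1 women wait for the laboratory result while POC is run alongside it. Before the move to phase 2, "correlation between POC and laboratory BhCG levels will be calculated in order to confirm its reliability by creating a correlation curve using the data". After that, "Patients in phase two will be provided with the POC test result", and the phase 2 aim is to give women their answer sooner, "with results and advice using point-of-care beta human chorionic gonadotrophin (BhCG) testing".

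No coefficient, threshold, bias estimate, limits of agreement or acceptable difference is stated. Section 6.1 (Statistics and data analysis) does not mention the comparison.

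Section 2.1 c describes the device as one that could provide "quick results that are comparable to hospital laboratory analysis" and adds: "This could therefore be used to risk stratify within a risk prediction model". Whether that happens in phase 2 is not stated.

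**The concern.** If women are to be given POC values, the question is whether a POC value is close enough to the laboratory value for the same woman. That is agreement. A correlation coefficient asks whether women with higher laboratory values also have higher POC values. If POC is wrong by the same factor in everyone, the ranking and the linear relation are intact and the coefficient does not move. It also depends on how widely levels vary between women, which has nothing to do with the device.

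Two things are at stake: the reliability purpose of phase 1, and the soundness of the POC results given out in phase 2. A high coefficient could be taken as a pass when a bias is present, and nothing written down would say otherwise.

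**Working it through.** **What the plan fixes.** It gives no sample size for the method comparison. The nearest figure is the 62 women per phase in section 6.1, which was set for anxiety rates of 32% against 10% (error 0.05, power 80%, 1:1). It reproduces:

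- Two-sided, uncorrected: n = [1.96·√(2·0.21·0.79) + 0.8416·√(0.32·0.68 + 0.10·0.90)]² / 0.22² = 52.6, so 53.
- With continuity correction: n = (52.6/4)·[1 + √(1 + 4/(52.6·0.22))]² = 61.4, so 62.

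I therefore take 62 time-zero pairs.

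**What is assumed.** The documents give no POC scatter, bias, spread of levels or acceptance range. I use scatter (CV) of 5%, 10% and 15%; bias of none, 10% low and 30% low; a log SD of 1.0 between women; and, for illustration, an acceptance range of 0.80 to 1.25.

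**Step 1: correlation ignores proportional bias.** Write POC = b × laboratory × error. On the raw scale b multiplies the covariance and the POC SD alike and cancels. On the log scale b is an added constant and drops out. With s = √ln(1 + CV²), the log-scale correlation is r = SD/√(SD² + s²), which does not contain b. At 10% scatter s = 0.0998, so r = 1/√(1 + 0.0998²) = 0.995 for any b.

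**Step 2: limits of agreement do respond.** The limits for the POC/laboratory ratio are b·exp(±1.96s). At 10% scatter:

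| Bias | r | Limits of agreement | POC more than 20% from laboratory |
|---|---|---|---|
| none | 0.995 | 0.82 to 1.22 | 4.6% |
| 30% low | 0.995 | 0.58 to 0.85 | 91% |

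The last column is Φ[(ln 0.8 − ln b)/s] + 1 − Φ[(ln 1.2 − ln b)/s].

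**Step 3: precision with 62 pairs.** The standard error of a limit is s·√(1/n + 1.96²/(2(n − 1))) = 0.218s, so the 95% CI half-width is 0.43s. At 10% scatter without bias, the lower limit 0.82 has a CI of 0.79 to 0.86, and the upper limit 1.22 has a CI of 1.17 to 1.27. An agreement analysis is feasible at the planned size.

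**Step 4: how a pass rule would behave.** Simulation with 62 pairs, range 0.80 to 1.25, 200,000 runs:

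| Scatter | Bias | Both point estimates inside | Both CIs inside as well |
|---|---|---|---|
| 5% | none | 100% | 100% |
| 5% | 10% low | 97% | 47% |
| 10% | none | 83% | 14% |
| 10% | 10% low | about 0.01% to 0.02% | 0% |
| 15% | none | 0.1% | 0% |

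With a 30% low bias the pass rate is 0% at every scatter. The rule detects what correlation misses, but the result depends heavily on how the rule is worded and how wide the range is.

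**The case against.** The strongest reply is that the harm is easily overstated. Most of it stands, and it limits the point in four ways.

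- **POC replacing the laboratory.** A reader might infer that phase 2 care rests on POC values alone. The documents do not say so. Section 4.9 d lists the 20 ml routine venous sample and the separate 1 ml POC sample without distinguishing phases, and section 7 says that research blood is taken together with routine blood. Laboratory BhCG may still be run in phase 2 and could correct a POC value later. The documents do not confirm this either.
- **POC being inaccurate.** Nothing in the documents suggests it. Section 2.1 c reports lab-quality results, regulatory approval and a CE mark. The 30% bias above illustrates a blind spot and does not estimate an error. But that section is background: the protocol chose to confirm reliability in its own unit, and the method should be able to do so.
- **The curve.** A plot of paired values could reveal a uniform 30% shift to an attentive reader. That is fair, but no one has said what shift would be too large.
- **Scatter.** A reader might argue that one coefficient can hide very different scatter. Across populations it can: r = 0.995 arises from 5% scatter at log SD 0.5 and from 15% at log SD 1.5. Within one study the spread of levels is observed, so scatter can be recovered from it and r. The real single-study gap is constant bias.

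The flowchart is not shown, so the reading rests on the text available.

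**Conclusion.** The point holds in a limited form. Correlation with a curve is the only stated method for confirming POC reliability before women receive POC results. Because it is blind to constant proportional bias, it cannot by itself confirm agreement. This is a choice of the wrong measure as well as missing detail.

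The size of any actual error is unknown and may be small; every error figure above is assumed. The blindness to bias does not depend on those figures. A reader might infer that the study's psychological result is at risk. It is not: HADS scores do not depend on this check, and POC reliability is not among the objectives in section 3 or the outcome measures in section 5. Use of POC values in the risk model during phase 2 is possible but unstated, so the point does not rest on it.

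**What to change.** In section 4.9, replace correlation as the criterion with:

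> Using one time-zero pair per woman, the mean POC/laboratory ratio (bias) and 95% limits of agreement will be estimated on the log scale, with 95% CIs. Reliability is confirmed if the point estimates of both limits lie within a range agreed with the laboratory before the paired data are viewed; the CIs are reported to show precision. The correlation curve is descriptive.

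Also state whether laboratory BhCG is still run in phase 2 and whether POC values enter the risk model.

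The analysis uses pairs that phase 1 already collects, so the computing cost is small. The real costs are agreeing a range and a possible delay to phase 2. Under the illustrative range of 0.80 to 1.25, a device with 10% scatter and no bias would still fail about 17% of the time (100% − 83%). It would almost always fail with a 10% low bias, and would fail about 86% of the time without bias if the CIs had to fit too. The unit should settle the range and the rule with these figures in view. Recruitment is already under way, so if the pairs have been viewed before the range is set, the report should say so.

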2.2 Study rationale and study hypothesis

a. Study rationale

PUL is a syndrome of early pregnancy composed of a positive urine pregnancy test without the visualisation of a pregnancy on trans-vaginal ultrasound (TVUS). The current method for risk stratifying a PUL is via serum BhCG levels at the time of identification of PUL and after 48 hours, in order to ascertain the viability of the pregnancy. Patients and their partners need to wait for this result before a management plan can be adopted, taking at least 2-3 hours.

There is a clear need for the patient care pathway to evolve in order to aid and improve the management of women classified with a PUL. By using point-of-care BhCG testing, we would shorten the time to management. We propose that shortening the time interval would reduce psychological morbidity.

b. Study hypothesis

- 1) PUL causes significant psychological distress to patients and their partners which can be assessed using a validated psychological tool.
- 2) Increasing the efficiency of PUL management will reduce anxiety and depression symptoms in patients and their partners.

3. Study Objectives

This study aims to improve the pathway of care to this cohort of women by:

- Assessing the psychological impact of pregnancy of unknown location (PUL) classification pending a final diagnosis.
- Assessing psychological burden of PUL on patients and their partners.

· Assessing if shortening time to providing patients classified with PUL with results and advice using point-of-care beta human chorionic gonadotrophin (BhCG) testing reduces psychological burden.

4. Methodology and Design

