c. Assessment of psychological symptoms

Patients diagnosed with PUL and their partners will be offered to take part in the study. Participants will be asked for written consent prior to point-of-care BhCG testing and completion of the HADS tool. The HADS tool takes 2-5 minutes to complete [22].

d. Clinical intervention

Performed in EPU as part of PUL classification:

- Transvaginal ultrasound
- 20ml venous blood sample

Performed in EPU or on the gynaecology ward following consent to participate in study:

- HADS tool
- 1ml sample of blood for point-of-care BhCG testing

e. Cataloguing

All data collection will be compliant with the Data Protection Act. The pseudonymised details will be logged onto a protected database with access restricted to only those personnel involved in the study. The data will be archived for secondary analysis.

Patients will be followed up for the duration of their care in the Early Pregnancy Unit. There will be no additional visits planned for research purposes.

Patients would remain in the study for a maximum of 2 months allowing time for final diagnosis and relevant follow up following intervention.

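### The time-zero HADS is tied to the blood draw but not to disclosure of the BhCG result, so a slightly delayed form is pre-result in phase 1 but may be post-result in phase 2

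*Combined protocol and SAP*

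**What the plan says.** Section 4.9 (Method of study) schedules the first HADS "On classification of PUL at time zero once blood is taken", the second at 48 hours after blood is taken (where 48-hour bloods are needed), and the third after diagnosis and management. On delivery it says: "The questionnaires for the first two time points will be offered electronically whilst the patient is having their blood sample taken". On return it says only: "The results will be submitted electronically each time". The limit of three contact attempts applies to the third form alone. Part c of the same section adds: "The HADS tool takes 2-5 minutes to complete". It places consent before both POC testing and the HADS, but does not order the HADS against the result.

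The result reaches women at different speeds in the two phases. In phase 1 the POC value is withheld and women wait for the laboratory. Section 2.2 says that patients and partners "need to wait for this result before a management plan can be adopted, taking at least 2-3 hours". In phase 2 the POC value is given to them, and section 2.1 c describes a test that "uses whole blood to provide lab-quality, quantitative results in minutes".

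Nothing in the text available requires submission before disclosure, records which came first, or says how a form completed after the result is handled. Appendix 12.1 lists a pathway flow chart, whose content is not in that text.

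**The concern.** The instruction for the time-zero form is the same in both phases, but its meaning can depend on phase, and phase is the exposure being compared for hypothesis 2. QR code delivery at the draw fixes when the form is offered, not when it is submitted. A woman who opens the link a little later has in phase 1 almost certainly not heard her result. In phase 2 she may have.

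If that happens, the time-zero score is a pre-result measurement in phase 1 and a mixture of pre- and post-result measurements in phase 2. Used as an outcome, it compares different states. Used as a starting value, it already carries any effect of early disclosure in one phase only. No HADS is taken before it, so there is nothing to fall back on. The 48-hour form is offered in the same way and shares the ambiguity. If the time of disclosure is not logged, no later analysis can sort the forms.

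**Working it through.** **The plan's own figure.** The only computed figure is the sample size in section 6.1. This point does not dispute it, but it supplies the 62 per phase used below. With 32% v 10%, two-sided 5% and 80% power:

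- Uncorrected: n = [1.96 × √(2 × 0.21 × 0.79) + 0.8416 × √(0.32 × 0.68 + 0.10 × 0.90)]² / 0.22² = (1.129 + 0.467)² / 0.0484 ≈ 52.6, so 53.
- With continuity correction: (52.6/4) × [1 + √(1 + 4/(52.6 × 0.22))]² ≈ 61.4, so **62**, as stated.

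The 47 partners per phase reproduce in the same way from 30% v 6%.

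**Timing, from the stated durations.** Let t be the time from draw to submission. A form is pre-result if t is shorter than the time to disclosure.

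- Opened at the draw and finished in 2-5 minutes: at least 120 − 5 = 115 minutes before the laboratory result in phase 1. In phase 2 it is probably also before the POC result, but both are measured in minutes.
- Submitted 20 minutes after the draw (an example): still at least 100 minutes before the laboratory result in phase 1. In phase 2 it falls on either side of disclosure, depending on what minutes means in practice, which the documents do not quantify.

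Every t between the POC disclosure time and the laboratory disclosure time gives a form that is pre-result in one phase and post-result in the other.

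**Illustration A: score scale (all inputs assumed except n = 62).** SD 4.5; correlation ρ = 0.6 between time-zero and later scores; true reduction with POC of 2 points; a share f of phase 2 time-zero forms submitted after the result; disclosure lowers those scores by d points. The baseline-adjusted effect is then 2 − ρ × f × d.

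| f | spurious time-zero gap, d = 2 | effect, d = 2 | effect, d = 1 | effect, d = 0.5 |
|---|---|---|---|---|
| 25% | 0.5 | 1.70 | 1.85 | 1.93 |
| 50% | 1.0 | 1.40 | 1.70 | 1.85 |
| 75% | 1.5 | 1.10 | 1.55 | 1.78 |

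With d = 2 and f = 50%, correlations of 0.4 and 0.8 give 1.6 and 1.2.

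Standard error: 4.5 × √(1 − 0.36) × √(2/62) ≈ 0.65. Power by the normal approximation is about 87% with no late forms and, for d = 2, about 75%, 58% and 40% at f = 25%, 50% and 75%. A simulation of 4000 runs gave 85%, 73%, 57% and 38%.

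The sign can reverse. If disclosure raises distress by 1 point (d = −1), then at f = 50% the adjusted effect is 2 + 0.6 × 0.5 × 1 = 2.3, an overstatement.

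**Illustration B: proportion scale.** Assume, as an extreme, that disclosure moves moderate-to-severe anxiety from 32% to 10%. These are the planning rates, but section 6.1 gives them as early pregnancy complications v controls, not as an effect of disclosure. The phase 2 time-zero rate is 0.32 − 0.22f: 26.5%, 21%, 15.5% and 10% at f = 25%, 50%, 75% and 100%. The gap from phase 1 caused by timing alone is 5.5, 11, 16.5 and 22 percentage points.

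**The case against.** The strongest reply is that the procedure already points to a pre-result form. A 2-5 minute questionnaire handed over during the draw and opened at once is finished about when the draw ends. Running the assay is also not the same as disclosing its result, since blood results are entered into a model and given with advice. The missing flow chart or the phase-specific information sheets may set the order. This stands in part: it makes early completion the likely intention and leaves the late share unknown. But the available text neither requires nor checks that order.

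A second reply concerns the size of the effect. A reader might infer that time zero is the study's baseline and that the plan stands to lose power from about 85% to 38%. The documents do not support that. They never call time zero a baseline, and section 5 lists it as one of three assessments. They specify no covariance or change-from-baseline analysis. A direct comparison of the later scores is untouched by late time-zero forms. The 2-point drop equals the whole assumed POC effect, although section 2.1 describes a single hCG as a poor predictor and the unit's model uses the 48-hour ratio. A time-zero value may therefore settle little. This objection stands in full: the power figures illustrate a mechanism and are not a property of this plan.

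Third, at 48 hours late phase 2 forms would shift that visit's own comparison. If results relieve distress, they would enlarge the apparent benefit, so the two visits need not err in the same direction. That also stands, and it is a reason to record timing rather than to presume a sign.

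**Conclusion.** The point holds as a gap in measurement timing. The plan anchors the time-zero HADS to the draw, the interval from draw to result differs between phases by design (minutes v at least 2-3 hours), and nothing places the form before disclosure. One written rule can thus yield pre-result forms in phase 1 and mixed forms in phase 2.

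The frequency, size and direction of any bias cannot be determined from the documents. They depend on how quickly women submit, how quickly POC results are actually given, whether a result lowers or raises distress, and how the three time points are analysed, none of which is stated. A reader might infer that misalignment will happen or that the comparison is invalid; neither follows. The sample size is unaffected. This is an inexpensive improvement worth making, because the information cannot be recovered later if the times were not logged.

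**What to change.** In section 4.9 (Method of study):

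- Keep the time-zero HADS after the draw, and add that it is to be submitted before any BhCG result is disclosed, with the same wording in both phases.
- At the time-zero and 48-hour visits, record the electronic submission time and the time the result was given.
- Flag any time-zero form submitted after disclosure as post-result and do not treat it as a pre-result score. Report the number of such forms by phase, with a sensitivity analysis that includes them. They would fall mainly in phase 2, so dropping them without comment would create missing data that differ by phase.
- For the 48-hour form, record and report by phase whether it was pre- or post-result, and leave its place in the visit as it is.

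Moving the forms to before the draw is tempting but not advised. Section 4.9 (Study closure) says patient recruitment has begun, so a change of position now could itself create a difference between earlier and later forms. A pre-draw 48-hour form would also miss that visit's wait, which POC testing is meant to shorten.

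The cost is one sentence of protocol text and one logged time per attendance; submission is already electronic, so its time should be available. Giving the phase 2 result might be delayed by a few minutes for study purposes, only where the clinical team finds that acceptable. Where the result is given first, the form is simply flagged.
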